4.9. Analysis Populations

For purposes of analysis, the following analysis sets are defined:

- **Screened Population Master Protocol:** All participants who complete informed consent for the master protocol
- **Screened Population Upamostat PSA:** All participants who complete informed consent for the upamostat PSA
- **Full Analysis Population:** All participants completing the second randomization step (randomization to a PSA).
 - The Full Analysis Population will be used for summaries of baseline demographic and clinical variables.
- **Modified Intention to Treat (mITT) Population:** All participants randomized who receive at least one dose of the IP/control.
 - The mITT population will be used for the primary efficacy assessment and for all other secondary efficacy analyses.

- **Safety Population:** All participants who receive at least one dose of the IP/control. In the unlikely case a participant receives the incorrect study drug, participants will be grouped according to the treatments that they received.
 - The Safety Population will be used in the analysis of the safety data.
- **Per Protocol Population:** All participants in the mITT set who completed treatment with IP/control and without major protocol deviations that impact the primary efficacy evaluation.
 - Prior to study unblinding, protocol deviations will be reviewed and a determination of the population for per protocol analysis will be made.
 - Participants will be excluded from the Per Protocol Population
 - Molnupiravir use
 - Missing 3 or more days of IP (determined by returned pill count of ≥ 8 or treatment discontinuation prior to Study Day 11).
 - The PP analysis population may be used for secondary and exploratory endpoints.
- **Baseline COVID-19 PCR Positive Population:** All participants in the mITT Population who have a positive baseline COVID PCR result.
 - The Primary and Secondary Outcome analyses will be repeated with the Baseline COVID-19 PCR Positive analysis population.

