Endpoints:	
Primary:
 
Time to sustained alleviation or resolution of COVID-19 symptoms [Timeframe: Day 0 to Day 28]
 
Secondary:
 
 • Change in overall COVID-19 symptom severity score [Timeframe: Day 0 to Day 28] • Proportion of participants in each treatment group developing new COVID-19 symptoms graded as severe on the symptom score [Timeframe: Day 0 to 28] • Proportion of participants who report: 
 ○ Return to usual state of health ○ Return to usual activities [Timeframe: Days 7, 14, 28 Week 8, and Week 12]

	
 • Proportion of participants hospitalized for COVID-19 [Timeframe: Day 0 to Week 12] • Number and proportion of participants hospitalized (all cause) • Number and proportion of death (all cause) • Comparison of active and placebo treatment groups in time to negative PCR [Timeframe: Day 0 to Week 12] 
Safety:
 
 • Incidence of Serious Adverse Events (SAE) • Comparison between active and placebo treatment groups in proportion of all and \geqgrade 3 adverse events as assessed by the National Institutes of Health, Division of AIDS Table for Grading the Severity of Adult and Pediatric Adverse Events (DAIDS AE Grading Table), corrected Version 2.1, July 2017. • Incidence of AEs causing IP discontinuation • Incidence of all-cause IP discontinuation or interruption • Incidence of Adverse Events of Special Interest (AESI) (if applicable to PSA) • Number of participants hospitalized due to adverse events regardless of cause 
Exploratory:
 
 • Assay for anti-SARS-CoV-2 IgM and IgG baseline and Week 8 • Targeted analysis of polymorphism of known host transmembrane proteases which may be involved in viral entry into host cells 	
Study Population:	Up to 300 SARS-CoV-2 infected adults	
Description of Sites/Facilities Enrolling Participants:	Ivory Coast	Abidjan: Institute Pasteur Bouake: Institut Pierre Richet / Institut National de Santé Publique
	Republic of South Africa	Bloemfontein: JOSHA Research Institute
	Thailand	Bangkok: Royal Thai Army
	Uganda	Fort Portal Regional Referral Hospital
	United [name]: Johns Hopkins Hospital Bayview Medical Center

Description of Study Intervention:	Upamostat Oral capsule : 400 mg (2×200 mg) daily for 14 days
Study Duration:	18 Months
Participant Duration:	12 Weeks

C 1.2 Schedule of Activities (SoA)

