 - Electrocardiographic evidence of complete LBBB, RBBB, incomplete LBBB, in complete RBBB
 - Evidence of second- or third-degree heart block
 - Intraventricular conduction delay with QRS duration > 120 msec
 - Bradycardia as defined by sinus rate < 50 bpm
 - Personal or family history of long QT syndrome
 - Personal history of cardiac disease, symptomatic or asymptomatic arrhythmias, except for sinus arrhythmia
 - Syncopal episodes or additional risk factors for torsades de points (e.g., heart failure, hypokalemia)

C 6.3 Lifestyle Considerations

Lifestyle Considerations as specified in the Master Protocol and:

- 1. Participants that engage in sexual activity that may lead to pregnancy in their partner must agree to either remain abstinent or use male contraceptives. They are also strongly advised to inform their non-pregnant sexual partners of reproductive potential to use effective contraceptives for 8 weeks after investigational agent is administered.**
- 2. Participants should refrain from sperm donation for 8 weeks after investigational agent administration.**
- 3. Upamostat may increase the sedative effects of alcohol so participants are encouraged to avoid alcohol while taking the study medication.**

C 7 STUDY INTERVENTION

C 7.1.1 Study Intervention Description

Upamostat is designated chemically as ethyl 4-{3-[(E)-amino(hydroxyimino)methyl]-N-[(2,4,6-triisopropylphenyl) sulfonyl]-L-phenylalanyl}-piperazine-1-carboxylate hydrogen sulphate.

C 7.1.2 Dosing and Administration

Upamostat 400 mg will be dosed orally once daily for 14 days.

C 7.2 Preparation/Handling/Storage/Accountability

C 7.2.2 Acquisition

Upamostat and placebo will be provided by RedHill either directly or through a third-party clinical supply distributor.

C 7.2.4 Formulation, Appearance, Packaging, and Labeling

Size 1 oral capsules contain a white to yellowish powder of 200 mg upamostat or placebo and are packaged in round white, 40 cc 33-400 wide-mouth marlex bottles with a white 33mm child resistant polypropylene cap with an induction seal at 30 capsules per bottle.

A standard label will be adhered to each bottle. Participants will be assigned to receive their treatment according to the randomization. For each cohort, randomized subjects will be assigned a unique number.

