The unique number will be the only participant identifier used on all sample collections and return of results. The site's blinded pharmacist or qualified designee will provide each participant with study drug and instructions for use; the initial doses for Day 0 will be given at the site.

C 7.2.5 Product Storage and Stability

Investigational drug must be kept in an appropriate, limited-access, secure place at controlled room temperature 15° to 25°C (60° to 77°F) and protected from light until it is used or returned to the industry supporter or designee for destruction. Investigational drug must be stored under the conditions specified on the label and remain in the original container until dispensed. A daily temperature log of the drug storage area must be maintained every working day while the drug is still in the research unit.

C 7.2.6 Preparation

All bottles provided contain 30 capsules of 200 mg upamostat or placebo and are prelabelled according to country specific requirements. 1 bottle will be dispensed to each participant at Day 0.

C 7.4 Measures to Minimize Bias: Randomization and Blinding

C 7.4.1 Randomization

Once randomized to the upamostat early treatment indication, participants will undergo a second, blinded randomization to either upamostat or placebo through the Interactive Voice/Web Response System (IxRS). Probability of randomization will be dependent on the number of products enrolling in the early treatment indication at that time.

The ratio of assignment to upamostat or placebo will be r:1 where r is the number of IPs concurrently enrolling in the early treatment indication that a given participant is eligible to receive. For example, if two products are enrolling in the treatment indication simultaneously, the probability of randomization of an eligible participant to upamostat or placebo will be 2:1. See also [Section C 13 Statistical Considerations](#).

The site research pharmacist(s) will be responsible for maintaining secure access to randomization assignments through the IxRS.

C 7.4.2 Blinding and Unblinding

Both participants and study investigators will be blinded to this second randomization.

Refer to the Master Protocol regarding unblinding.

C 7.6 Concomitant Therapy

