4.10. Derivations, Data Handling Conventions and Missing Data

Baseline will be defined as the last assessment prior to the first dose date/time (or randomization if patient was not treated).

Study Day will be derived as (assessment date – date of first dose) + 1.

Event durations in days will be derived as (end date – start date) + 1.

Missing data will not be imputed unless otherwise specified elsewhere in this SAP. Missing dates or partially missing dates will be imputed conservatively for adverse events and concomitant medications. Specific rules for the handling of missing or partially missing dates for adverse events and concomitant medications are provided in Appendix A A.

By-visit endpoints will be analyzed using observed data unless otherwise specified. For observed data analyses, missing data will not be imputed, and only the observed records will be included.

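### The Per Protocol rule's two tests for 3 missed days disagree: with the first dose as Study Day 1, the date test starts at 4 missed days

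*SAP*

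**What the plan says.** SAP 4.9 limits the Per Protocol population to mITT participants who completed treatment and had no major deviation bearing on the primary efficacy evaluation. It then lists specific exclusions. One is "Missing 3 or more days of IP", and a parenthesis says how this is established: "determined by returned pill count of ≥ 8" or "treatment discontinuation prior to Study Day 11".

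SAP 4.10 fixes the day count: "Study Day will be derived as (assessment date – date of first dose) + 1". The first-dose date is therefore Study Day 1, and there is no Study Day 0.

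The dosing inputs are in Protocol Appendix C:
- C 7.1.2: "Upamostat 400 mg will be dosed orally once daily for 14 days".
- C 1.1: "400 mg (2×200 mg) daily for 14 days", so two capsules a day.
- C 7.2.6: "All bottles provided contain 30 capsules of 200 mg upamostat or placebo", with one bottle dispensed per participant.
- C 7.2.4: the first dose is given at the site on protocol Day 0.
- C 12.1: where therapy is paused and resumed, the skipped days are not added at the end.

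**The concern.** The parenthesis offers two measurements of a single threshold, 3 missed days, so both should place the cut at the same exposure. Under the SAP's definition of Study Day they do not. The date test asks for at least one more missed day than the capsule test.

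The date test matters most when the capsule count is absent or unreliable, and that is where its threshold departs from the stated one. Two participants with the same exposure, each taking the last dose on Study Day 11, are treated differently by the explicit rule: the one with a counted bottle is excluded, and the one without is not caught. The Per Protocol population is used to repeat the primary analysis (SAP 5.2.1), the overall symptom severity analysis (SAP 5.2.2) and time to negative PCR (SAP 5.2.3).

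**Working it through.** **Inputs.** 14 daily doses, 2 capsules a day and one bottle of 30 capsules (Protocol C 7.1.2, C 1.1, C 7.2.6). First dose = Study Day 1 (SAP 4.10) or protocol Day 0 (Protocol C 7.2.4). Stated threshold: 3 missed days (SAP 4.9).

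**Capsule test, reproducing the stated figure.** Full compliance uses 14 × 2 = 28 capsules and leaves 30 − 28 = 2.

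Missed days = 14 − (30 − returned) / 2.
- 8 returned: 14 − 22/2 = 14 − 11 = 3.
- 7 returned: 14 − 23/2 = 14 − 11.5 = 2.5.

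The cut at 8 capsules corresponds to 3 missed days, as the SAP says.

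**Date test.** For a participant who takes every dose until stopping:
- counting from Study Day 1, doses taken = last-dose day;
- counting from Day 0, doses taken = last-dose day + 1;
- missed days = 14 − doses taken;
- capsules returned = 30 − 2 × doses taken.

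The SAP does not say whether discontinuation is dated to the last dose or to the first day without one, so both are shown. Each row describes the latest stopper whom the cut at day 11 catches.

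| Day count | Discontinuation dated to | Latest last dose caught | Doses | Missed | Capsules returned |
|---|---|---|---|---|---|
| Study Day (first dose = 1) | last dose | 10 | 10 | 4 | 10 |
| Study Day (first dose = 1) | first undosed day | 9 | 9 | 5 | 12 |
| Protocol day (first dose = 0) | last dose | 10 | 11 | 3 | 8 |
| Protocol day (first dose = 0) | first undosed day | 9 | 10 | 4 | 10 |

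Only the third row gives 3. Under the SAP's defined term the minimum is 4 or 5.

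**The participant in the gap.** Last dose on Study Day 11: 11 doses, 14 − 11 = 3 missed, 30 − 22 = 8 capsules returned. The capsule test excludes this participant and the date test does not. If discontinuation means the first undosed day, a last dose on Study Day 10 (4 missed, 10 returned) falls in the same gap.

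**The case against.** Five points can be made for the SAP.

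1. *Day 0 numbering is in use.* A reader might infer that the date test rests on a day count foreign to the SAP. It does not. The SAP's endpoint timeframes start at Day 0 (SAP 3.1, 3.2, 5.2.1, 5.2.2), and SAP 4.10.2 places the baseline PCR on Day 0. On that count, with discontinuation dated to the last dose, the two tests agree. This stands: the likely origin is Day 0 numbering carried into a rule worded with the defined term. It explains the mismatch without removing it, because Study Day is the term that SAP 4.10 defines and a programmer would follow.

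2. *The general definition may catch the participant anyway.* It is tempting to say that someone who stops after Study Day 11 without returning a bottle is kept in the population. The documents do not establish that. SAP 4.9 first requires completed treatment, and a permanent early stopper may fail that requirement. The blinded deviation review (SAP 4.6 and 4.9) also determines membership, and diary-reported doses are collected (SAP 5.1.3). But completion is not defined and the diary is not named as a criterion in the rule. If completion excluded every early stopper, the date test would have no work to do. These points soften the consequence and leave the inconsistency in place.

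3. *The tests are joined by 'or'.* Anyone with a returned and counted bottle is classified at 3 days. This is correct, and it confines the gap to participants without a usable count.

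4. *Dependence on bottle return is inherent in a capsule count.* A participant with scattered missed days and no bottle cannot be classified by either test, and aligning the date would not change that. The day-count mismatch should not be blamed for it.

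5. *The main result is unaffected.* Correct. The primary analysis uses the mITT population.

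**Conclusion.** The inconsistency is real and minor. As worded, SAP 4.9 states one threshold of 3 missed days and gives two tests for it. The capsule test meets the threshold. Under SAP 4.10 the date test starts at 4 missed days, or at 5 if discontinuation is dated to the first undosed day. No passage in either document reconciles them. The intended threshold is not in doubt; the fault lies in day numbering and an undefined discontinuation date.

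On the last-dose reading, the affected participants are those whose last dose was exactly on Study Day 11 and who have no usable capsule count. The documents give no figure for how many that might be. The explicit rule would not catch them; whether they would finally be in or out depends on the undefined completion requirement and the blinded review. Only the Per Protocol repeat analyses are touched, so nothing here supports a claim that the primary result is biased.

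The conclusion assumes one dose a day without gaps until stopping, one bottle of 30, and Study Day read as SAP 4.10 defines it.

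**What to change.** Before unblinding, make both tests mean 3 or more missed days. Either wording does it:

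- last dose on or before Study Day 11, that is, discontinuation prior to Study Day 12, with Study Day as in SAP 4.10; or
- keep the cut at day 11 and state that, for this rule, days are counted from Day 0 and discontinuation is the date of the last dose.

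It would also help to add a sentence saying whether the requirement to have completed treatment means anything beyond this rule.

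The cost is a line or two of SAP text and the matching line in the population program. Version 1.0 was signed on 28 July 2025, after enrollment had ended, so the change belongs in SAP Appendix A with its timing relative to unblinding. The documents do not say whether the blinded data review has taken place. If it has, the Per Protocol list should be rechecked, still blinded, for last doses on Study Days 10 and 11 without a capsule count. The change concerns the definition of an analysis population only and implies nothing about dosing or stopping rules.

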4.10. Derivations, Data Handling Conventions and Missing Data

Baseline will be defined as the last assessment prior to the first dose date/time (or randomization if patient was not treated).

Study Day will be derived as (assessment date – date of first dose) + 1.

Event durations in days will be derived as (end date – start date) + 1.

Missing data will not be imputed unless otherwise specified elsewhere in this SAP. Missing dates or partially missing dates will be imputed conservatively for adverse events and concomitant medications. Specific rules for the handling of missing or partially missing dates for adverse events and concomitant medications are provided in Appendix A A.

By-visit endpoints will be analyzed using observed data unless otherwise specified. For observed data analyses, missing data will not be imputed, and only the observed records will be included.

4.10.1. Resolution of Symptoms

The primary analyses will be based on an intent-to-treat approach. Therefore, every patient in the mITT Population will be analyzed. A single imputation approach for each patient with missing data will be utilized with a range of sensitivity analyses exploring the sensitivity of the results to the missing data.

A single imputation approach will be conducted for the primary analysis for each patient with missing daily observations. The following single imputation will be utilized:

- If the patient's last day was symptom free, then the patient will be assumed symptom free, and their time of resolution will be the first symptom free day.
- If the patient's last day was symptoms alleviated, then the patient will be assumed symptom alleviated and their time of alleviation the first day of alleviated symptoms.
- If the patient's last day was non-alleviated or resolved symptoms, they will be assumed censored without alleviation or resolution at the last observed day.

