1. INTRODUCTION

This statistical analysis plan (SAP) expands Section 13 (Statistical Considerations) of the master protocol “Master Protocol for Early Treatment and Post-Exposure Prophylaxis of COVID-19 Adaptive Platform Trial” (PROTECT-APT 1) and Section C 13 (Statistical Considerations) of the Product Specific Appendix (PSA) “Appendix C: A Phase 2 Safety and Efficacy Study of Upamostat for Early Outpatient Treatment of COVID-19”. The final SAP approval by the sponsor will occur before data unblinding. Any changes to the planned analysis will be documented in the Clinical Study Report (CSR).

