5.2. Efficacy Assessments

The key efficacy assessment in the early treatment indication is time to sustained alleviation or resolution of symptoms among patients who were SARS-CoV-2 positive on initial screening at a local laboratory, either by PCR or rapid antigen test. Time to sustained alleviation or resolution of targeted COVID-19 symptoms will be defined as the number of days from randomization in a PSA (Step 2 of randomization) to the first day the participant reports all symptoms as mild or none (≤ 1 on the Daily Follow Up Symptom Questionnaire), or no worse than the usual severity, for at least 3 consecutive days (the first day being considered the Event Day).

Targeted symptoms include stuffy or runny nose, hoarse voice, sore throat, difficulty breathing, cough, fatigue, muscle or body aches, headache, chills or shivering, feeling hot or feverish, nausea, vomiting, diarrhea, loss of taste, loss of smell. The Symptom Severity Score is collected in the Symptom Follow Up Questionnaire as the Overall Symptom Severity. Overall Symptom Severity may be rated none (0), mild (1), moderate (2), or severe (3). Loss of taste and loss of smell may be rated as the same as usual (0), less than usual (1), or no sense of taste/smell (2, considered a “severe” rating).

The general statistical approach will compare outcomes among participants randomized to receive the active agent, upamostat, to outcomes among participants who were eligible to have been randomized to upamostat but who were randomized instead to any of the placebo arms enrolling at that time. This ensures that the comparison is limited to concurrently randomized participants eligible to receive upamostat.

Unless otherwise specified, for each analysis, a 5% two-sided significance will be used. 95% confidence intervals will be presented to summarize each effect estimate. Dichotomous outcomes will be summarized with relative proportions. Ordinal outcomes will be summarized with stacked bar plots, cumulative proportion graphs, and percentiles. Kaplan-Meier plots will be used for summarizing time to event outcomes. Continuous measures will be summarized with box plots (means, medians, and inter-quartile ranges).

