Sustained alleviation or resolution will be defined as the number of days from randomization within a PSA to the first day the participant reports all symptoms as mild or none (≤ 1 or returning to pre-illness levels) for at least 3 consecutive days (the first day being considered the Event Day). Targeted symptoms will be used for analysis (Supplement 3). Symptoms will be collected at Enrollment using the Screening Symptom Questionnaire to establish baseline symptom status.

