5.2.1. Primary Outcome

- Time to sustained alleviation or resolution of COVID-19 symptoms evaluated from Day 0 through Day 28 assessed via completion of a Daily Follow Up Symptom Questionnaire
 - Analysis population: mITT

The primary objective is to estimate the relative time to sustained alleviation or resolution of symptomatic COVID-19 infection for a participant that receives upamostat compared to a participant that does not receive upamostat.

The primary analysis population is the Modified Intent-to-Treat Population.

The estimand of interest is the hazard ratio of a participant that has symptomatic COVID-19 with standard of care background therapy when starting treatment with upamostat compared to no upamostat. A hazard ratio greater than 1 indicates a shorter time to resolution of symptomatic COVID-19 infection

The primary analysis model is a Cox proportional hazards model for the time to alleviation or resolution of COVID-19 symptoms, with treatment arm (active upamostat vs placebo) as a fixed

covariate with proportional effect. The model estimated hazard ratio will be used as the estimator for the estimand of interest. The estimate and 95% confidence interval for the hazard ratio will be presented.

The primary hypothesis test is that upamostat increases the hazard (decreases time to resolution) of COVID-19 symptoms. A hypothesis test will be conducted for testing whether the upamostat hazard ratio is greater than 1 at a one-sided 2.5% level.

Additional sensitivity analyses for the primary analysis will utilize additional covariate adjustments in the Cox proportional hazards model. The analysis will be repeated for the Per Protocol Population and the Baseline COVID-19 PCR Positive Population.

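### The missing-diary rule in SAP 4.10.1 can give the primary event a different date from the endpoint definition, or censor an event that was observed

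*SAP*

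**What the plan says.** SAP 5.2 counts days from Step 2 randomization to "the first day the participant reports all symptoms as mild or none" (a score of 1 or less, or no worse than usual), and this must hold "for at least 3 consecutive days (the first day being considered the Event Day". SAP 3.1 and protocol C 13.5.1.1 define the event in the same way. None of them requires a complete diary.

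SAP 4.10.1 then sets the rule for missing data: "A single imputation approach will be conducted for the primary analysis for each patient with missing daily observations". Three bullets follow, each decided by status on the participant's last day:

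- Symptom free: an event, and "their time of resolution will be the first symptom free day".
- Alleviated: an event, dated at the first alleviated day.
- Neither: if the "last day was non-alleviated or resolved symptoms, they will be assumed censored", at the last day observed.

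The same section promises the single imputation "with a range of sensitivity analyses exploring the sensitivity of the results to the missing data". The only such analyses that SAP 5.2.1 names are these: "Additional sensitivity analyses for the primary analysis will utilize additional covariate adjustments in the Cox proportional hazards model". It adds repeats in the per-protocol and baseline PCR-positive populations.

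**The concern.** The bullets do not carry the endpoint definition forward. The first uses a stricter state (symptom free) than the endpoint (mild or none). None contains the 3-day requirement. Nothing limits the rule to participants whose event is still unknown when the diary stops.

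This is the primary derivation. Two programmers who follow SAP 5.2 and 4.10.1 in good faith could give the same diary different event days, or a different event status. On the literal reading, a day skipped long after recovery changes the result. No sensitivity analysis named in the SAP varies the missing-diary rule, so none would reveal this.

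**Working it through.** **The plan's own figures.** The documents attach no number to this rule. The design figures reproduce, so the design is not in question. The interim alpha is 0.025 × 0.5² = 0.00625, and the final nominal alpha is 0.02178, as stated. With 150 per arm, a control median of 9 days and a hazard ratio of 1.50, expected events are 150(1 − e^(−28 ln2/9)) + 150(1 − e^(−1.5×28 ln2/9)) = 276.7. Two-look power is then 0.915 (protocol Table 3: 0.906). At a hazard ratio of 1.42 it is 0.819 (Table 3: 0.812).

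**Step 1: score example diaries.** Each was scored under the definition, under the literal text of 4.10.1, and under the fix proposed below.

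| Diary | Definition | 4.10.1 literal | Fix |
|---|---|---|---|
| A. Moderate Days 1–4, mild 5–9, none 10–28; Day 20 skipped | Day 5 | Day 10 | Day 5 |
| B. First mild on Day 5, none on Day 6, then missing | no run observed | Day 6 | Day 5 |
| C. Mild Day 3, moderate 4–10, mild 11, then missing | no run observed | Day 3 | Day 11 |
| D. Moderate Days 1–4, mild 5–26, moderate 27–28; Day 20 skipped | Day 5 | censored Day 28 | Day 5 |

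Without the skipped day, A and D are both events on Day 5. A and D go wrong only if the rule overrides an observed run. B and C have no observed run, so they go wrong even if the rule is confined to diaries that stop early. In C the event is dated before a seven-day relapse.

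**Step 2: how many participants the literal rule reaches.** Assume days are skipped independently with probability p over 28 diary days. The proportion with at least one gap is 1 − (1 − p)^28:

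- p = 1%: 1 − 0.99^28 = 0.245
- p = 2%: 1 − 0.98^28 = 0.432
- p = 5%: 1 − 0.95^28 = 0.762

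**Step 3: effect on the hazard ratio.** Two simulations were run, both with missingness equal in the two arms.

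*First model.* This is a daily three-state model with 20,000 per arm, all starting moderate, and Cox regression with Efron ties. Moderate-to-mild is h = 8.0–10.5% per day, set to give a control median of 9 days, with 1 − (1 − h)^1.5 in the active arm. Assumed daily rates are 10 or 30% mild-to-none, 5 or 15% mild-to-moderate, and 3% none-to-mild.

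- Literal reading, 1–5% of days skipped: the hazard ratio falls from 1.46–1.50 on complete diaries to 1.35–1.45. The shift is 0.02–0.07 at 1%, 0.03–0.08 at 2% and 0.05–0.12 at 5%. Among affected participants with an observed run, 4–25% are scored censored. Of those still scored as events, 66–84% are dated later, by 3–7 days on average.
- Literal reading, 10 or 30% of diaries stopping on Days 4–21 and no skips: the shift is 0.00–0.02.
- Dropout-only reading with observed runs kept, 10–30% stopping early: the change is below 0.01. About 7–10% of stoppers are credited from a good last day without a run, and 5–18% of those are dated late. That is 0.07 × 0.05 = 0.35% to 0.10 × 0.18 = 1.8% of stoppers.
- Proposed fix, with a skipped day breaking a run: within about 0.01 of the complete-diary value.

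*Second model.* This uses 150 per arm, exponential times, an assumed 5-day mean lag from mild to none, and 150 replicates, so Monte Carlo error is not small. It compares the literal rule with keeping observed runs, at 1%, 2% and 5% skipping.

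- No late relapse: the hazard ratio goes from 1.50 to 1.48, 1.42 to 1.40 and 1.47 to 1.43. The control median goes from about 9.7 to 11.1, 9.4 to 11.9 and 9.9 to 14.0 days.
- 5% late relapse: the hazard ratio goes from 1.51 to 1.47, 1.47 to 1.42 and 1.48 to 1.39. Power falls by about 2, 7 and 12 points.

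**The case against.** The best defence is that the rule was meant only for diaries that stop before a 3-day run. Its references to a last day and a last observed day suggest dropout. SAP 4.10 makes non-imputation the default, and an observed run is not missing data. A careful programmer would derive observed events first. On that reading the effect on the hazard ratio is negligible.

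Part of this stands. The intention is plausible, and the larger figures depend on the literal reading. But the text sets no such limit, and 4.10.1 is itself the exception that SAP 4.10 allows for. The next section, 4.10.2, shows how a limit can be written: its allowance for a single negative PCR applies only when that result is the final one collected. Diaries B and C are misdated even on the narrow reading.

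Several points on size also stand:

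- The upper shifts need high assumed relapse. With relapse of 0–1% per day, censoring of observed runs falls to 0–3%. The literal shift is then about 0.01–0.02 when mild-to-none is fast and 0.04–0.08 when it is slow.
- Skips concentrated in some participants would lower the 25%, 43% and 76% figures.
- With equal missingness the shifts are toward 1, so they show attenuation and lost power, not a route to false success.
- The wording of the third bullet, which could be read to censor a resolved last day, is a copy-edit.
- The Master Protocol, which the SAP also expands, is not among the documents reviewed and may say more on sensitivity analyses.

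Crediting an event from a good last day after dropout is an assumption and not in itself an error.

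**Conclusion.** The concern holds. As written, 4.10.1 contradicts the primary endpoint definition on event dating and, read literally, lets one missing day override an observed 3-day run. That conclusion comes from the text and does not depend on the simulations.

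The size for this trial cannot be derived, because no missing-diary rate is given. Under the assumed inputs, the literal reading moves the hazard ratio toward 1 by about 0.02–0.12, and by as little as 0.01 where relapse is rare. With observed runs kept, the change is at most about 0.02 in any of the checks made. The effect is negligible or moderate depending on which reading is programmed, so the text should settle it. It should be fixed.

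**What to change.** Replace the three bullets with the following:

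1. An observed run of at least 3 consecutive days with all targeted symptoms at 1 or below (or at usual level) is the event. It is dated at its first day and stands whatever follows or is missing later.
2. Imputation applies only to participants with no such run.
3. For them, if the last state is carried forward, date the event at the first day at 1 or below in the final unbroken run up to the last diary day, whether that day is mild or symptom free. If the last observed day is not alleviated, censor there.
4. State how a skipped day inside a run is handled. For example, it breaks the run, with a sensitivity version in which one skipped day between two days at 1 or below counts as 1 or below.
5. Name as a missing-data sensitivity analysis the version that censors at the last observed day when no run was observed. Making that version primary and carry-forward the sensitivity analysis is a defensible alternative, at the price of slightly fewer events.

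Report by arm the number with any missing diary day and the number scored by imputation.

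The cost is an amendment to a SAP signed as v1.0 on 28 July 2025, plus derivation code. If the trial is still blinded, log the change in Appendix A with its relation to unblinding. If it is already unblinded, report both derivations in the study report, in line with SAP section 1: "Any changes to the planned analysis will be documented in the Clinical Study Report (CSR".
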